5.7. Medical and Psychiatric History

Medical and psychiatric history events will be mapped to a Medical Dictionary for Regulatory Activities (MedDRA) versions 27.0 and 27.1 preferred term and system organ class. Medical and psychiatric history will be summarized by treatment group for the ITT Analysis Set using preferred terms and system organ classes. All events will be listed for the ITT Analysis Set.

5.8. Exposure to Treatment

The number of participants who received IMP, number of days on IMP, number of treatment discontinuations, reasons for treatment discontinuation, and treatment compliance will be summarized by treatment group for the FAS: Expanded Analysis Set. Drug accountability data will be listed.

5.9. eDiary Compliance

Primary, secondary, and other efficacy variables are based on diary-collected panic attack frequencies, and as such, diary compliance will be evaluated along with treatment compliance. Participants are instructed to complete their diary entries at least once a day during the study. A diary day will be considered missing for compliance if a panic attack diary record is missing for that day. Diary compliance will be evaluated during the Screening Period, the Baseline Period, the Titration Period, the Maintenance Period, the entire Treatment Period, and the last two weeks of Maintenance Treatment.

eDiary compliance will be calculated as 100 times the number diary days (days with diary completed) during the period and dividing this quantity by the expected number of diary days that should have been completed during this period of time. Compliance is computed for actual time of participation in the study through Visit 8 follow-up. If a participant did not enter an analysis period, the diary compliance for the analysis period will not be calculated.

eDiary compliance data will be listed by treatment then participant for each diary type and summarized by treatment group and version of diary used.

5.10. Mini International Neuropsychiatric Interview

Participants MINI summary will be listed.

5.11. Primary Efficacy Analysis

5.11.1. Primary Analysis

The primary estimand has the following attributes:

1. Treatments as randomized
2. The population defined by the inclusion/exclusion criteria of the trial as the primary population of interest
3. The proportion of participants who are free of panic attacks during the last two weeks of the Maintenance Treatment as the primary endpoint of interest
4. The population level summary of interest is the estimated odds ratio of freedom from panic attack between treatments and the corresponding 95% confidence intervals (CI)
5. Handling of intercurrent events (ICEs)
 - The treatment policy strategy will be used to handle the ICE of use of concomitant medications during the study for primary analysis of the primary efficacy endpoint, which will include the collected data in the analyses regardless of the use of medications
 - The hypothetical strategy will be used to handle the ICEs of discontinuation from treatment/study participation for primary analysis of the primary efficacy endpoint, which will only include collected data through the discontinuation visit

5.11.2. Main Analytical Approach

The number and proportion of participants who are free of panic attacks during the last two weeks of the Maintenance Treatment will be summarized by analysis period and treatment group. The binomial repeated measures will be analyzed using the SAS[®] GENMOD procedure with logit link. The Baseline PDSS total score will be included as a covariate, and the treatment group, analysis periods, evidence-based psychotherapy use, and interaction between treatment group and analysis period will be included as fixed effects. Model diagnostics will be performed to explore the goodness-of-fit. An unstructured covariance matrix will be used for the repeated measures model. If the sparseness of the data results in model convergence or other issues, affecting reliability of estimates, efficacy conclusions will be based on the sensitivity analysis using the Fisher's exact test described in [Section 5.11.3](#). The odds ratio of active dose to placebo at the endpoint analysis period will be estimated based on the least squares mean difference in logit between the treatment groups from the GENMOD model with the associated 95% CI and p-values.

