### 9.3.2. Primary Endpoint/Estimand Analyses

The primary estimand has the following attributes:

1. Treatments as randomized
2. The population defined by the inclusion/exclusion criteria of the trial as the primary population of interest

3. The proportion of participants who are free of panic attacks during the last 2 weeks of the Maintenance Treatment Period as the primary endpoint of interest
4. The population level summary of interest is the estimated odds ratio of freedom from panic attack between treatments and the corresponding 95% CI
5. A composite strategy will be used to address missing values due to ICEs regardless of whether they are considered as treatment related. Specifically, participants who fail to achieve panic free in the last 2 weeks of treatment prior to ICE, including cases of missing all post-baseline assessments (other than for logistic reasons such as randomization errors) in the FAS defined in [Table 7](#), will be considered as failure.

The number and proportion of participants who are free of panic attacks during the last 2 weeks of the Maintenance Treatment Period will be summarized by visit and treatment group. The binomial repeated measures will be analyzed using the SAS® GLIMMIX procedure with logit link. The Baseline PDSS total score will be included as a covariate, and the treatment group, visits, evidence-based psychotherapy use, and interaction between treatment group and visit will be included as fixed effect. Model diagnostics will be performed to explore the goodness-of-fit. An unstructured covariance structure will be used for the repeated measures. If the unstructured covariance matrix results in convergence issue, a structured covariance matrix such as the heterogeneous Toeplitz structure may be used. In the case that a structured covariance matrix needs to be used, a robust sandwich variance estimator will be used. The odds ratio of active dose to placebo at the endpoint visit will be estimated based on the least squares mean difference in logit between the treatment groups from the GLIMMIX model with the associated 95% CI and p-values. A sensitivity analysis using Fisher's exact test and 95% exact CI will be performed to assess the robustness of the conclusion from the logistic regression and the impact of potential use of a structured covariance matrix on the estimation of treatment effect.

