1.2. Sample Size Considerations

A sample size of 114 participants per group (total of 228 participants) will provide at least 80% power to detect a difference of approximately 20% in proportion of participants (e.g., 60% of darigabat group versus 40% of placebo group) free of panic attacks at Week 14 at $\alpha=0.05$ (2-sided).

Two-hundred forty-six participants will be randomized to account for 18 participants whose panic attack assessments were made prior to implementation of protocol eDiary requirements (i.e., assessments recorded contemporaneous to the day being assessed [minimizing any potential recall bias] and records of the presence as well as the absence of each DSM-5-TR panic attack symptom associated with a given panic attack [distinguishing between missing data and the absence of a specific symptom]).

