5.11.3. Sensitivity Analyses

A sensitivity analysis using Fisher's exact test and 95% exact CI about the difference in treatment groups will be performed to assess the robustness of the conclusion from the logistic regression and the impact of potential use of a structured covariance matrix on the estimation of treatment effect.

Participants will be assessed based on the final two weeks of treatment in the Maintenance Period. Those with less than 12 eDiary days and no reported panic attacks will be imputed as missing.

Additional sensitivity analysis will include the model-based analysis described in [Section 5.11.2](#) conducted using all participants regardless of panic attack eDiary version used.

Lastly, two sensitivity analyses will be performed using modified definitions of the efficacy endpoint, free of panic attacks. Under the first modified definition, a participant is considered to be panic free within a two-week interval if during each two-week interval, there are no missing eDiary days and there is no presence of panic attacks associated with 4 symptoms as specified in DSM-5-TR. The second definition will require 10 or more eDiary days without a reported panic attack (per DSM-5-TR). The outcome for participants who do not report a panic attack associated (per DSM-5-TR) but have missing eDiary days, will be considered missing for efficacy analysis. Analysis using the model-based approach described in [Section 5.11.2](#) will be performed using the 14/14 eDiary day definition and the Fisher's exact test will be performed using the both modified definitions.

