6. CHANGES IN THE PLANNED ANALYSES

Analysis methods described here reflect revisions to strategic focus and scope and will supersede those described in the protocol. In addition to changes corresponding to protocol amendments, the analysis plan differs from the statistical analysis section of the protocol as described below:

- As a result of early closure of enrollment and early treatment discontinuation of ongoing participants, planned sample size will not be achieved and proportion of participants with treatment discontinuation will be increased. The resulting sample size will have insufficient power for hypothesis tests and thus, efficacy analysis will be exploratory.
 - The following changes were made to the protocol-specified statistical analysis to reflect the strategic shift to an exploratory evaluation of efficacy
 - Multiplicity adjustments were removed
 - Most sensitivity analyses were removed
 - Supportive analyses involving panic attack-related endpoints were added using an expanded FAS population including all participants regardless of eDiary version used
- Description of handling of ICEs was expanded and revised for the primary and key secondary endpoints:
 - Additional detail was provided for different types of ICEs (eg, administration of rescue medication and treatment discontinuation)
 - Composite strategy was replaced with treatment policy and while on treatment strategies for handling ICEs for analysis of primary and key secondary endpoints
- Added description of missing diary data handling:
 - For the primary efficacy outcome (proportion of participants free of panic attacks), outcome for participants who did not report a panic attack and had <12/14 days of completed eDiary was set to missing, unless otherwise indicated
 - For key secondary efficacy outcome (change from baseline in the frequency of panic attacks), outcome for participants with <7/14 days of completed eDiary was set to missing
- The SAP replaced the SAS® procedure GLIMMIX (specified in protocol) with GENMOD to fit binomial repeated measures model to estimate the proportion of participants that were free of panic attack and the treatment difference. Although both procedures can fit binomial repeated measures model, model-fitting is more efficient with the GENMOD procedure.

Should any deviations from the analyses pre-specified in the authorized statistical analysis plan arise, such deviations will be documented in the final clinical study report.

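### The primary panic-free model drops straight to an unadjusted Fisher test on an open-ended trigger, with the protocol's intermediate covariance step removed

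*SAP*

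**What the plan says.** Protocol 9.3.2 specifies GLIMMIX with a logit link and an unstructured covariance. If that does not converge, a structured covariance (heterogeneous Toeplitz is the example) may be used: "In the case that a structured covariance matrix needs to be used, a robust sandwich variance estimator will be used". Fisher's exact test is a sensitivity analysis only.

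SAP 5.11.2 replaces GLIMMIX with GENMOD and keeps the unstructured matrix, the baseline PDSS covariate, psychotherapy use and the treatment-by-period interaction. It offers no structured alternative. If sparse data lead to "model convergence or other issues, affecting reliability of estimates, efficacy conclusions will be based on the sensitivity analysis", the test in question being Fisher's.

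SAP 5.11.3 describes that test with an exact interval for the difference between groups, and says it will also assess "the impact of potential use of a structured covariance matrix on the estimation of treatment effect". SAP 5.11.1 names the odds ratio as the population summary.

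SAP section 6 lists the change of procedure, on the ground that "model-fitting is more efficient with the GENMOD procedure". It lists neither the removal of the structured step nor the new role of Fisher's test as a possible basis for conclusions.

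**The concern.** There are three linked problems.

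- **The trigger is open.** Non-convergence is a fact that anyone can check. The second limb, unspecified problems with reliability, is a judgement with no threshold. Because the model includes treatment and its interaction with period, that judgement is made on a fit that also displays the treatment estimate and its p-value.
- **A step is missing.** Failure of one covariance structure is a reason to try a simpler one, not to abandon the adjusted model. With generalised estimating equations (GEE), which is what repeated measures in GENMOD amounts to, a sandwich variance remains valid when the working correlation is simplified.
- **The fallback answers a different question.** It moves from an adjusted odds ratio using all periods to a crude difference in one window.

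At stake are the credibility of whichever result is put forward and, if the fallback is used, some of the limited information left after early closure.

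**Working it through.** **1. The fallback rules side by side.**

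| Place | If the unstructured fit fails | Role of Fisher's test |
|---|---|---|
| Protocol 9.3.2 (panic-free) | structured covariance with sandwich variance | sensitivity only |
| SAP 5.11.2 (panic-free) | straight to Fisher's test | can carry the conclusions |
| SAP 5.11.3 (panic-free) | still presumes a structured matrix may be used | sensitivity |
| SAP 5.12.1.2 (PDSS) | Fisher scoring for starting values, heterogeneous Toeplitz, heterogeneous AR(1), with sandwich variance | none |

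So 5.11.2 and 5.11.3 do not agree, and the SAP keeps for PDSS the kind of ordered fallback that it removes for the primary endpoint.

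**2. Size of the unstructured matrix.** SAP Table 3 has six two-week maintenance intervals. Correlations: 6 × 5 / 2 = 15. SAP section 6 expects a smaller sample and more discontinuation than planned.

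**3. The plan's own power figure.** SAP 1.2 says that 114 per group "will provide at least 80% power to detect a difference of approximately 20% in proportion of participants", for example "60% of darigabat group versus 40% of placebo group", at two-sided 0.05. Pooled normal approximation:

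z = (0.20 − 1.96 × √(2 × 0.5 × 0.5 / 114)) / √((0.6 × 0.4 + 0.4 × 0.6) / 114) = (0.20 − 1.96 × 0.0662) / 0.0649 = 1.08, so power is 86.0%.

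Exact enumeration gives 86.9% for chi-square and 83.8% for Fisher. The stated floor of 80% holds.

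**4. Cost of Fisher's test at smaller numbers.** The documents give no final sample size, so 30, 40 and 60 evaluable per arm are assumptions. For every pair of counts (a, b), sum Bin(a; n, p1) × Bin(b; n, p2) over the pairs that the test rejects at two-sided 0.05. Size uses p1 = p2 = 0.40; power uses 0.60 and 0.40.

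| n per arm | Fisher size | Chi-square size | Fisher power | Chi-square power | Power gap (points) |
|---|---|---|---|---|---|
| 30 | 2.6% | 4.9% | 25.7% | 35.0% | 9.3 |
| 40 | 3.0% | 5.2% | 36.9% | 45.8% | 8.9 |
| 60 | 3.2% | 5.1% | 54.0% | 61.2% | 7.3 |
| 114 (plan) | 3.6% | 5.0% | 83.8% | 86.9% | 3.1 |

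**5. How the adjusted model behaves.** Simulation with assumed inputs: six periods, latent correlation 0.6, one baseline covariate, either no dropout or 26 to 33% missing at the last period, 800 runs per setting.

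- Unstructured GEE failed to fit in 0 to 1 of 800 runs at 114 per group and in 2 to 28 of 800 at 50 per group (28/800 = 3.5%).
- With no dropout, or dropout following the same rule in both arms, GEE alone rejected a true null in 5.4 to 7.9% of runs. Taking whichever of GEE and Fisher gave the smaller p-value raised this to 5.9 to 9.2%, an increase of 0.5 to 1.5 points within each setting. Simulation error on a 5% rate is √(0.05 × 0.95 / 800), about 0.8 points.

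Free choice of test is the worst case, not what the SAP permits. GEE's tendency to exceed 5% is the reason for asking for a small-sample correction.

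**The case against.** The strongest reply is that the rule is narrower than it looks. It is tied to sparse data, names a single destination that is conservative, and sits in a SAP to be finalised before unblinding. SAP section 6 concedes insufficient power and calls efficacy exploratory, and 5.4 drops multiplicity control. The chi-square comparator in the table is not a planned test, and power is lost only if the fallback is used. All of that is fair, and it limits the consequence. It does not supply a criterion for the trigger or explain why the intermediate step was removed.

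A reader might infer more than the documents support:

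- **That the GENMOD analysis is invalid.** The SAP states no missing-data mechanism; MAR and MNAR appear only in its abbreviation list. Unweighted GEE is not guaranteed under missing-at-random dropout, but the bias found was small. Under the null, the simulation in step 5 gave log odds ratios of −0.002 to 0.003. A harsher scenario, with placebo dropout of 12 to 20% per interval after panic against 2% after a panic-free interval and 6 to 10% on active regardless, gave odds ratios of 1.03 to 1.10. Since ln 1.10 = 0.095 and the standard error at 60 per arm with 50% response is √(4/60 + 4/60) = 0.37, that is about a quarter of a standard error. Discontinuations caused by the sponsor's closure may also be unrelated to outcome.
- **That moving from GLIMMIX gave up a likelihood-based method.** The protocol's wording also fits a marginal pseudo-likelihood model, and the unstructured matrix was already in the protocol.
- **That convergence failure is likely.** At most 3.5% of fits failed at 50 per group.
- **That the Fisher fallback carries the bias of a completers-only comparison.** SAP 5.11.3 uses each participant's final two weeks on maintenance treatment, so completer figures do not describe it.

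**Conclusion.** The point holds as a defect of specification. The trigger has no objective test and is judged on a fit containing treatment. That this happens after unblinding is inference, since the SAP names neither timing nor decision-maker. The structured-covariance step was removed without being listed, and 5.11.3 was not brought into line. If used, the fallback changes the summary measure, discards covariates and repeated data, and costs 7 to 9 points of power against chi-square at an assumed 30 to 60 per arm (about 3 at the planned 114). Inflation from choosing between tests was modest, 0.5 to 1.5 points, under the assumed settings without arm-dependent dropout. With efficacy exploratory, this should be corrected, but it does not overturn the analysis.

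**What to change.** - In SAP 5.11.2, replace the open second limb of the trigger with criteria stated in advance: non-convergence, a working correlation that is not positive definite, or an empty arm-by-period cell.
- Fix the order as unstructured, exchangeable, then independence working correlation, each with a small-sample-corrected sandwich variance, and report which step was reached.
- Keep Fisher's test as a sensitivity analysis. Let it carry conclusions only if every step fails, as it may when the empty cell is in the endpoint period, which no working correlation can repair.
- Amend 5.11.3 to match, and list the change in section 6.
- State the missing-data assumption behind the hypothetical strategy, and add weighted GEE or multiple imputation as a sensitivity analysis.

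The cost is SAP wording, a little more SAS code and one dropout model. Simpler working correlations may be somewhat less efficient and more exposed to missing-at-random dropout, which is a further reason for the added analysis. Dropout weights will not cover everything: under SAP 3.1.1.2 an interval with fewer than 12 diary days is missing only when no attack was reported, so that missingness depends on the current outcome.

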5.11.3. Sensitivity Analyses

A sensitivity analysis using Fisher's exact test and 95% exact CI about the difference in treatment groups will be performed to assess the robustness of the conclusion from the logistic regression and the impact of potential use of a structured covariance matrix on the estimation of treatment effect.

Participants will be assessed based on the final two weeks of treatment in the Maintenance Period. Those with less than 12 eDiary days and no reported panic attacks will be imputed as missing.

Additional sensitivity analysis will include the model-based analysis described in [Section 5.11.2](#) conducted using all participants regardless of panic attack eDiary version used.

Lastly, two sensitivity analyses will be performed using modified definitions of the efficacy endpoint, free of panic attacks. Under the first modified definition, a participant is considered to be panic free within a two-week interval if during each two-week interval, there are no missing eDiary days and there is no presence of panic attacks associated with 4 symptoms as specified in DSM-5-TR. The second definition will require 10 or more eDiary days without a reported panic attack (per DSM-5-TR). The outcome for participants who do not report a panic attack associated (per DSM-5-TR) but have missing eDiary days, will be considered missing for efficacy analysis. Analysis using the model-based approach described in [Section 5.11.2](#) will be performed using the 14/14 eDiary day definition and the Fisher's exact test will be performed using the both modified definitions.

5.12. Key Secondary Efficacy Analyses

5.12.1. First Key Secondary Analyses

5.12.1.1. Estimand

The first key secondary estimand has the following attributes:

1. Treatments as randomized
2. The population defined by the inclusion/exclusion criteria of the trial as the primary population of interest
3. The change from baseline in PDSS total score at Week 14 as the endpoint of interest
4. The population level summary of interest is the estimated treatment differences and the corresponding 95% confidence interval based on a mixed model for repeated measures (MMRM)
5. Handling of intercurrent events (ICEs)
 - The treatment policy strategy will be used to handle the ICE of use of concomitant medications during the study for primary analysis of the primary efficacy endpoint, which will include the collected data in the analyses regardless of the use of medications
 - The hypothetical strategy will be used to handle the ICEs of discontinuation from treatment/study participation for primary analysis of the primary efficacy endpoint, which will only include collected data through the discontinuation visit

5.12.1.2. Analytic Method

The change from Baseline to each trial visit in PDSS total score will be summarized by visit and treatment group. An MMRM analysis will be used with fixed effects of treatment group, visits, evidence-based psychotherapy use, and interaction between treatment group and visit. The baseline value of PDSS total score will be included as a covariate. Participant will be included as a random effect. An unstructured covariance structure will be used for the repeated measures. The Kenward-Roger approximation will be used to estimate the denominator degrees of freedom. If the unstructured covariance matrix results in convergence issue, the Fisher scoring algorithm may be used to obtain the initial values of covariance parameters. If convergence issues still cannot be resolved, a structured covariance matrix may be used with the heterogeneous Toeplitz covariance structure followed by the heterogeneous first-order autoregressive (AR[1]) structure. In the case that a structured covariance matrix needs to be used, a robust sandwich variance estimator will be used to address the potential adverse impact of covariance matrix misspecification. The difference between active dose and placebo at the endpoint visit will be estimated based on the least squares mean difference between the treatment groups at the endpoint visit from the MMRM with the associated 95% CI and p-values. The LS Mean (\pm SE) from the model will be plotted for change in PDSS total score during each visit by treatment group. Similarly, the mean (\pm SD) of absolute values and change from Baseline PDSS total score will be presented by visit and treatment group.

